Artificial intelligence in the characterization of colorectal polyps: A prospective study in a clinical setting using CAD EYE®

STUDY PROTOCOL

[name], [name], [name]

October 29th, 2020

Artificial intelligence in the characterization of colorectal polyps: A prospective study in a clinical setting using CAD EYE®

[name], [name], [name]

Gastroenterology Department, Centro Hospitalar e Universitário de Coimbra, E.P.E.,
Coimbra, Portugal

STUDY PROTOCOL

Brief summary

Current guidelines recommend resection and histopathological analyses of all colorectal polyps. Real-time optical diagnosis can obviate non-neoplastic polyp resection (“diagnose-and-leave-behind”) and histopathological analyses of diminutive polyps (“predict-resect-and-discard”) reducing healthcare and cost burden. The investigators aimed to evaluate the diagnostic accuracy of computer-aided diagnosis using CAD EYE® (Fujifilm, Germany) in real-time optical characterization of colorectal polyps compared to endoscopic diagnosis with histopathology as the gold-standard. For this purpose, a single-centre prospective study of diminutive/small colorectal polyps is ongoing.

Introduction

Worldwide, colorectal cancer (CRC) is the 4th most frequent cancer and the 3rd cause of cancer-related death. In Portugal, CRC is the 3rd most common cause and the 2nd leading cause of cancer-related mortality. In colorectal carcinogenesis, colorectal polyps (adenomatous or serrated polyps) are considered premalignant lesions. The detection of colorectal polyps and subsequent resection is effective in reducing CRC incidence and mortality and the risk of interval CRC, and is the crucial aspect of CRC prevention. Considering the detection of colorectal polyps, there is a wide variation among endoscopists in terms of skills for the detection of adenomas, the major premalignant lesions of CRC, translated into the detection rate of adenomas (ADR). ADR is considered a marker of careful inspection of colorectal mucosa, translating quality in colonoscopy, which is inversely associated with the risk of interval CRC or cancer-related death. In the context of screening colonoscopy, the minimum ADR is 25% to reduce the risk of interval

CRC and death, being predictably higher if a positive fecal occult blood test is found, although the exact value still remains to be elucidated. The detection rate of serrated polyps has been strongly correlated with ADR.

About 50% of small polyps are non-adenomatous and these polyps have no malignancy potential, especially for small polyps, whose cancer risk is extremely low (0-0.6%). The resection of these non-adenomatous polyps may increase medical costs and risks related to post-polypectomy complications (bleeding, perforation).

Real time optical diagnosis by artificial intelligence can improve the cost-benefit and efficiency of colonoscopy as an auxiliary tool in the decision making of which polyps should be resected and which polyps should be recovered for histological characterization. However, its practical application implies a negative predictive value $\geq 90\%$ in optical diagnosis in order to don't have implications in terms of interval CRC and medico-legal issues.

CAD EYE® (Fujifilm, Europe, Gesellschaft mit beschränkter Haftung, Dusseldorf, Germany) is a fully-automated computer program, which allows the detection of colorectal polyps as well as their histological classification using the artificial intelligence technology using deep learning, so-called REill. When applied in a high-quality colonoscopy, it seems to improve the detection rate of polyps and the ADR in real time, during colonoscopy course. In fact, the detection of difficult lesions remains one of the major challenges in the endoscopy field in last years, particularly for flat lesions, multiple polyps and polyps located at the image periphery. The detection of colorectal polyps is shown by 3 simultaneous identifiers, 2 visual and 1 auditory. The visual identifiers correspond to a detection box in the area of suspected polyps and a semicircle at the periphery of the image, corresponding to the quadrant where the suspect polyps are located. The auditory stimulus corresponds to a volume adjustable sound signal emitted when a suspect polyps is detected. Regarding the optical characterization of histopathology, colo-rectal polyps are classified into 2 types, hyperplastic (green colour), which include hyperplastic and serrated polyps, and neoplastic (yellow colour), for adenomas and adenocarcinomas. In addition, it allows to perform this characterization in 3 confidence levels and the mapping of the position of the suspected area.

This system allows the storage of videos related to both detection and characterization of colorectal polyps, one of the recognized quality tools in colonoscopy.

The detection mode of colorectal polyps is performed in white light imaging (WLI) or Linked Colour Imaging (LCI), while the optical characterization is performed in Blue Light Imaging (BLI)

mode, without the need to fix or zoom the image. This tool is user-friendly, simple, intuitive and does not interfere with colonoscopy images.

Objectives

Primary objectives

- To evaluate the diagnostic accuracy of computer-aided diagnosis using CAD EYE[®] system in real-time optical characterization of colorectal polyps compared to digital chromoendoscopy;
- To evaluate the diagnostic accuracy of computer-aided diagnosis using CAD EYE[®] system in real-time optical characterization of colorectal polyps by comparison with histopathological analysis.

Secondary objectives

- To evaluate the diagnostic accuracy of computer-aided diagnosis using CAD EYE[®] system in real-time optical characterization of colorectal polyps in terms of dimension (≤ 5 , 6-9mm and ≥ 10 mm), location and histological type (hyperplastic, serrated sessile lesion, adenoma, adenocarcinoma);
- To evaluate the diagnostic accuracy of computer-aided diagnosis using CAD EYE[®] system in real-time optical characterization of colorectal polyps according to the experience of the endoscopist.

Population and methodology

Type of study

Prospective observational cohort study

Type of sample

The total number of consecutive patients who underwent elective colonoscopy with high quality of bowel preparation (at least two points per segment and at least of six points at the total score of Boston Bowel Preparation), performed at the Gastroenterology Department of the Centro

Hospitalar e Universitário de Coimbra, E.P.E., Coimbra, Portugal, with at least one identified colorectal polyp, regardless the indication for its performance.

Inclusion criteria

- Age ≥ 18 years
- The presence of at least one polyp in an elective colonoscopy

Exclusion criteria

- Poor bowel preparation (Boston Bowel Preparation Score < 6 at the total score or < 2 at one of colorectal segment)
- No recovery of excised polyps for histopathological analysis
- The presence of polyps not amenable to endoscopic excision or with contraindication for their excision at the time of colonoscopy
- The absence of explicit indication for colonoscopy

Study design

All colonoscopies will be performed by the endoscopist (trainee and experienced endoscopist) using CAD EYE[®] in detection mode (WLI or LCI), during colonoscopy retrieval. When a suspected polyp is identified by the endoscopist, optical characterization is performed by the endoscopist in WLI and BLI modes, in a first phase and by the CAD EYE[®] with BLI, in a second phase.

Methods plan

Phase 1. Brief virtual chromoendoscopy training on the characterization of colorectal polyps (WLI, LCI and BLI)

Phase 2. CAD EYE[®] system applied during colonoscopy retrieval:

2.1. CAD EYE[®] system OFF: Virtual chromoendoscopy (BLI) – independently characterization of a suspected polyp in WLI and BLI by the first endoscopist and by the second endoscopist (iconographic record)

2.2. CAD EYE® system ON: Characterization mode (BLI): Characterization of a suspected polyp by CAD EYE® and respectively level of characterization (1 to 3) (iconographic record)

Phase 3. Histopathological evaluation (pathologist with gastrointestinal expertise): Resection and recovery of a suspected polyp for anatomopathological characterization

Detailed explanation of Methods phases

Phase 1. Brief virtual chromoendoscopy training on the characterization of colorectal polyps (WLI, LCI and BLI)

Virtual chromoendoscopy training should be performed online through the BASIC e-learning platform (bli.eu/category/e-learning/). This training should be carried out by all participants enrolled in the project (trainees and experienced endoscopists) before its practical application, which will allow skills acquisition on the characterization of virtual chromoendoscopy of colorectal polyps using BLI. Additionally, a brief review of the Kudo classification of pit pattern of colorectal polyps should be carried out.

Phase 2. Evaluation of colorectal polyps in real-time - Optical characterization of colorectal polyps

The first approach on optical characterization of an identified polyp consists in the evaluation of the polyp, first in WLI mode and then in BLI mode, with CAD EYE® OFF. This evaluation should be systematically performed by two independent endoscopists in the exam room, and the evaluation of both should be recorded on a separate record sheet by the endoscopist who is not performing the examination. The two endoscopists should preferably (but not necessarily) be an experienced endoscopist and a trainee from the last few years, and the presence of at least one experienced endoscopist is mandatory. The independent evaluation is guaranteed by a phased and recorded approach: 1st step - The 1st endoscopist (endoscopist performing colonoscopy) request the polyp evaluation and written record by the 2nd endoscopist (the one who is not performing the colonoscopy) - blinded evaluation because the 1st endoscopist doesn't verbalize his evaluation); 2nd moment - when the 2nd endoscopist signals that he has completed his record, the 1st endoscopist verbally explicit his classification, which is recorded by the 2nd endoscopist. This evaluation should include the histopathological type of polyp (hyperplastic, adenoma, sessile serrated lesion or other type) and the level of confidence of the

evaluation performed (high or low). Kudo classification of pit pattern can also be recorded (optional).

Afterwards, optical characterization mode of CAD EYE® (CAD EYE® ON) in BLI mode should be activated for the evaluation of CAD EYE® optical characterization, in hyperplastic or neoplastic polyps, as well as the level of characterization (graduated from 1 to 3). The evaluation of the CAD EYE® should also be recorded by the endoscopist in the exam room who is not performing the colonoscopy, on its own record sheet.

The iconographic record of evaluated polyps in WLI and BLI modes and the evaluation video using CAD EYE® in BLI characterization mode should be done.

Phase 3. Histopathological evaluation (by pathologist with gastrointestinal expertise)

After detection and optical characterization of identified colorectal polyps, their resection should be performed by the most appropriate technique according to the size and type of polyp (cold forceps polypectomy if dimensions <3mm), cold snare polypectomy if dimension between 3-10mm and diathermic snare polypectomy/endoscopic mucosal resection if lesions >10mm) and recovery of colorectal polyp for anatomopathological characterization. Each colorectal polyp should be recovered to a separate vial. Unrecovered polyps will not be counted for comparative evaluation of optical characterization.

Statistical analysis

The diagnostic performance of CAD EYE® will be evaluated by comparison with the gold standard (histological characterization in the optical characterization phase), in terms of diagnostic accuracy, sensitivity, specificity, positive predictive value and negative predictive value. Sub-analysis can be performed regarding the size, location and histological type of polyp, as well as the expertise of the endoscopist.

Sample size calculation

For an alpha risk of 0.05 and beta risk of 0.2 for a bilateral test, it will be necessary to include 197 colorectal polyps assuming the initial pre-intervention diagnostic ratio is 0.7 and the final after-intervention ratio is 0.82.

Expected Results

It is expected that the new CAD EYE[®] system will have a diagnostic accuracy in the optical characterization of colorectal polyps around 78.4%, comparable to experienced endoscopists (78.4% vs 79.6%) and superior to less experienced endoscopists (70.7% vs 79.6%).(14) Thus, the new CAD EYE[®] system will allow optical characterization with high accuracy impacting as a decision making tool for the endoscopist in strategies based on optical diagnosis such as "diagnosis and leave behind" for diminutive polyps from sigmoid colon and rectum with high degree of confidence in hyperplastic histology and "predict, resect and discard" for diminutive polyps.

References

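### Polyps with an earlier histological result are eligible and neither endoscopist is blinded to it, so the CAD EYE versus digital chromoendoscopy comparison can tilt towards the endoscopist, by an unknown amount

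*Combined protocol and SAP*

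**What the plan says.** Under Type of sample, the protocol takes consecutive patients having an elective colonoscopy "with at least one identified colorectal polyp, regardless the indication for its performance". The matching inclusion criterion is "The presence of at least one polyp in an elective colonoscopy". It does not require the polyp to be newly found or not yet sampled.

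The Exclusion criteria cover poor bowel preparation, polyps not recovered for histology, "The presence of polyps not amenable to endoscopic excision or with contraindication for their excision at the time of colonoscopy", and "The absence of explicit indication for colonoscopy". None concerns earlier histology. A referral to remove a known polyp is itself an explicit indication, so it passes the last criterion.

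The first primary objective is the accuracy of CAD EYE "in real-time optical characterization of colorectal polyps compared to digital chromoendoscopy". The second compares CAD EYE with histopathology.

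On blinding, the detailed text for Phase 2 states: "The independent evaluation is guaranteed by a phased and recorded approach". The mechanism is that the second endoscopist writes a reading before hearing the first one's: "blinded evaluation because the 1st endoscopist doesn't verbalize his evaluation". Each endoscopist records a predicted histological type and a confidence level. CAD EYE is then switched on and its classification recorded. The protocol mentions no masking of the indication, earlier reports or earlier pathology, no record of prior knowledge, and no analysis that takes account of it.

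**The concern.** The endoscopist is asked to predict histology, and that is what an earlier biopsy report supplies. Where such a report exists and is known, the recorded optical diagnosis may combine the image with the report. The Introduction describes CAD EYE as an automated program, and Phase 2 applies it to the BLI view. No route is described by which it could use the patient's history.

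Prior histology can therefore raise the endoscopist's agreement with the reference standard but not CAD EYE's. In a head-to-head comparison on the same polyps this works in one direction, and recruiting more polyps does not remove it. As written, the plan would also leave no data from which anyone could show that the effect was negligible.

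**Working it through.** **1. The plan's own figure.** Sample size calculation gives 197 polyps for 0.70 versus 0.82, two-sided alpha 0.05, beta 0.2. The unpooled formula gives (1.960 + 0.842)² × (0.70×0.30 + 0.82×0.18) / 0.12² = 7.849 × 0.3576 / 0.0144 = 194.9, so 195. The pooled version gives 198, the arcsine version 196.03 (197), and a paired McNemar calculation with independent readings 200.4 (201). The 197 is reproduced to rounding, and the present point does not alter it.

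**2. Inputs for the bias.**
- Unaided endoscopist accuracy p: 78.4% or 79.6%, from Expected Results. That sentence is ambiguous. It puts CAD EYE at around 78.4%, yet it pairs 79.6% with both endoscopist groups. In the pair 70.7% vs 79.6%, where CAD EYE is said to be superior, 79.6% has to be CAD EYE. Both values are therefore carried.
- Share f of polyps with a known earlier histological result: not in the documents. Assumed 5%, 10%, 20%.
- Accuracy k when that result is known: not in the documents. Assumed 90% to 100%.

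**3. Formula.** Observed accuracy = (1 − f)·p + f·k, so inflation = f·(k − p).

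| p | k | f = 5% | f = 10% | f = 20% |
|---|---|---|---|---|
| 0.796 | 0.90 | 0.52 | 1.04 | 2.08 |
| 0.796 | 1.00 | 1.02 | 2.04 | 4.08 |
| 0.784 | 0.90 | 0.58 | 1.16 | 2.32 |
| 0.784 | 1.00 | 1.08 | 2.16 | 4.32 |

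Entries are percentage points. The range is about 0.5 to 4.3.

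**4. If these polyps are easier than average.** The p that matters is the unaided accuracy on these same polyps. If it were 90%, a 10% share would give 0.10 × (0.95 − 0.90) = 0.5 points at k = 95%, and between 0 and 1.0 points for k from 90% to 100%.

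**5. Against the sizing assumptions, conditionally.** The plan does not say which comparison 0.70 and 0.82 describe. If 0.70 were the endoscopist and 0.82 CAD EYE, a 10% share with k of 90-100% would lift 0.70 to 0.72-0.73 and cut the 12-point difference to 10-9 points. With paired power Φ[(d√197 − 1.960√π) / √(π − d²)], where π is the discordant proportion under independent readings, power falls from about 0.79 (d = 0.12, π = 0.372) to 0.65 (d = 0.10, π = 0.72×0.18 + 0.82×0.28 = 0.359) or 0.57 (d = 0.09). The conclusion does not rest on this step.

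**6. Which analyses are touched.** Statistical analysis evaluates CAD EYE against histology and then allows sub-analysis by size, location, histological type and expertise. The secondary objective on size is likewise about CAD EYE's accuracy. Neither uses the endoscopist's reading as the quantity estimated. Only the first primary objective sets the human reading beside CAD EYE.

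**The case against.** The strongest reply is that the mechanism is inferred. No section says that previously biopsied polyps are enrolled or that readers consult earlier reports. Study design describes polyps identified by the endoscopist with CAD EYE in detection mode, and the Brief summary describes a study of diminutive and small polyps. The provision for "diathermic snare polypectomy/endoscopic mucosal resection if lesions >10mm" matches technique to size and is not evidence of a referral stream. All of this stands. It means that the frequency is unknown, not that the gap is closed: the criteria admit such polyps, the size strata include 10 mm and above, and nothing masks the earlier result.

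The size can also fairly be called modest. On the plan's 12-point sizing difference, 1 or 2 points is small. At 197 polyps with independent readings, the 95% half-width for 78.4% versus 79.6% is 1.96 × √[(0.784×0.216 + 0.796×0.204)/197] = 1.96 × 0.041, or about 8 points. That is right for small shares, but a wide interval does not correct a shift in one direction.

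A reader might infer four stronger things that the documents do not support:
- That the size sub-analysis is distorted. It concerns CAD EYE against histology, which this route leaves alone.
- That every previously seen or photographed polyp carries the problem. Without an earlier histological result there is no pathology report to feed the reading.
- That the bias exceeds the expected 1.2-point gap (79.6 − 78.4) with experienced endoscopists. This depends on assumed shares, on k and on the polyps being of average difficulty, and the protocol is unclear on which side that gap lies.
- That all known targets and previous resection sites must be excluded from the study. This would change a consecutive, any-indication population and goes beyond what the bias requires.

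**Conclusion.** The point holds in a limited form. Followed as written, the plan can let an earlier histological result enter the endoscopist's reading but not CAD EYE's, which can bias the first primary objective towards the endoscopist. The second primary objective and the CAD EYE sub-analysis by size are unaffected.

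The direction follows from the design as described. The size does not: the range of about 0.5 to 4.3 points rests on an assumed 5-20% share, assumed accuracy of 90-100% when histology is known, and unaided accuracy of 78.4% or 79.6% on these polyps. It would be smaller if they are easy to read, and close to nil if almost all polyps are new. The change is worth making because it is cheap and because, without it, the size of the effect cannot be examined.

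**What to change.** - Add one field to the record sheet, completed before the optical reading: does this polyp have a previous histological result known to, or available to, either endoscopist?
- State in Statistical analysis that polyps marked yes are left out of the CAD EYE versus endoscopist comparison but kept for CAD EYE versus histology. Report the comparison with them included as a sensitivity analysis.
- The Brief summary describes the study as ongoing. For polyps already enrolled, set the flag from the referral record, without reference to the study readings, so that this later exclusion cannot depend on the results.

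Eligibility and the consecutive sample stay as they are. The cost is one extra field, a check of referral records for polyps already enrolled, and fewer polyps in one comparison: at the assumed shares of 5% to 20%, about 10 to 39 of 197 (197 × 0.05 = 9.9; 197 × 0.20 = 39.4). If the 197 is meant to size that comparison, count it on the polyps that enter it, which lengthens recruitment somewhat.

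### The first primary objective, CAD EYE versus the endoscopist's digital chromoendoscopy, has no between-method analysis, and neither of the two endoscopist reads is named as comparator

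*Combined protocol and SAP*

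**What the plan says.** **Objectives.** The first primary objective is CAD EYE's accuracy in "real-time optical characterization of colorectal polyps compared to digital chromoendoscopy"; the second is its accuracy against histopathology. The Brief summary joins the two: CAD EYE "compared to endoscopic diagnosis with histopathology as the gold-standard".

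**Statistical analysis.** CAD EYE's performance "will be evaluated by comparison with the gold standard (histological characterization in the optical characterization phase", by accuracy, sensitivity, specificity and predictive values. The endoscopist appears only in a sentence permitting sub-analyses, one of them by expertise.

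**Sample size calculation.** 197 polyps, two-sided alpha 0.05, beta 0.2, rates 0.70 and 0.82 labelled as before and after intervention. No test or reader is named.

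**Reads.** Phase 2.1 of the Methods plan calls for "independently characterization of a suspected polyp in WLI and BLI by the first endoscopist and by the second endoscopist". The detailed Phase 2 text fixes the modality, "first in WLI mode and then in BLI mode, with CAD EYE® OFF", but not the reader's experience: "The two endoscopists should preferably (but not necessarily) be an experienced endoscopist and a trainee from the last few years". At least one must be experienced. Study design allows either level to perform the examination: "All colonoscopies will be performed by the endoscopist (trainee and experienced endoscopist".

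**Classes.** The Introduction gives CAD EYE two outputs: "hyperplastic (green colour), which include hyperplastic and serrated polyps, and neoplastic (yellow colour), for adenomas and adenocarcinomas". Phase 2 has endoscopists record sessile serrated lesion separately from hyperplastic, with a further category for other types. The secondary objectives also list it as a separate histological type.

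**Expected Results.** CAD EYE is expected to match experienced endoscopists (78.4% vs 79.6%) and to exceed less experienced ones (70.7% vs 79.6%).

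**The concern.** The analysis section serves the second primary objective and leaves the first without a method. A statistician following it would compute CAD EYE's accuracy against histology and stop. Endoscopist accuracy, the difference between the methods and its uncertainty would not be produced.

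Anyone who does attempt the comparison must first pick a read. The performing, second (observing) and experienced reads are available for every polyp; a trainee read may not be. First and second reader do not map onto experience, because the pairing is only preferred. The document expects near-equality with experienced readers and superiority over less experienced ones, so the choice of read largely decides the answer. If it is made after the data are seen, the reported p-value no longer has its nominal error rate.

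A correct call is also undefined for this comparison: CAD EYE groups serrated with hyperplastic, while the endoscopist's record and the listed histological types keep them apart.

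**Working it through.** **1. The plan's own number.** Inputs from Sample size calculation: 0.70, 0.82, two-sided alpha 0.05, power 0.80.
- Two independent proportions, pooled: n = (1.96·√(2·0.76·0.24) + 0.842·√(0.70·0.30 + 0.82·0.18))² / 0.12² = 197.7 per group. The arcsine form gives 196.0.
- Paired test: n = (1.96·√ψ + 0.842·√(ψ − d²))² / d², where d = 0.12 and ψ is the share of polyps on which exactly one method is correct. With independent errors ψ = 0.70·0.18 + 0.82·0.30 = 0.372 and n = 200.4.

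So 197 reproduces. It is the size of a comparison between two rates, which the analysis section does not contain.

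**2. Gaps by reader**, from Expected Results. The text does not settle whether CAD EYE is 78.4% or 79.6%.
- Experienced: 79.6 − 78.4 = 1.2 points, in either direction.
- Less experienced: 78.4 − 70.7 = 7.7 points, or 79.6 − 70.7 = 8.9 points.

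**3. Chance of a significant difference at n = 197.** The documents give no within-polyp correlation r between the two methods' correctness, so r = 0, 0.3 and 0.5 are assumed. Clustering within patients is ignored.

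ψ = p₁ + p₂ − 2(p₁p₂ + r·√(p₁q₁p₂q₂)), with q = 1 − p; power = Φ((√n·d − 1.96√ψ)/√(ψ − d²)) plus the opposite tail.

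| Comparison | r = 0 | r = 0.3 | r = 0.5 |
|---|---|---|---|
| 78.4 vs 79.6 (experienced) | 6% | 6% | 7% |
| 70.7 vs 78.4 (less experienced) | 42% | 55% | 69% |
| 70.7 vs 79.6 (less experienced) | 53% | 68% | 81% |

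**4. Cost of leaving the read open.** 40,000 simulated studies of 197 polyps at each r, with CAD EYE and two readers all at an assumed accuracy of 0.78, and McNemar |z| > 1.96. One pre-named comparison is significant in 4.8 to 5.1% of studies; at least one of the two is significant in 8.8 to 9.3%.

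**5. Precision against an experienced read.** The 95% half-width is 1.96·√((ψ − d²)/n) with d = 0.012.
- r = 0: ψ = 0.332, giving 1.96·√(0.3317/197) = 0.080.
- r = 0.5: ψ = 0.166, giving 1.96·√(0.1659/197) = 0.057.

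The interval is therefore about ±5.7 to ±8.0 points around an expected gap of 1.2.

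**6. Why discordance should be stated.** For 0.70 vs 0.82 the paired formula needs 200.4, 142.8 and 104.4 polyps at r = 0, 0.3 and 0.5 (ψ = 0.372, 0.266, 0.196).

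**The case against.** The best reply is that the comparison is plainly intended. It is in the Brief summary and the objectives, Phase 3 refers to a comparative evaluation, the sample size rests on two rates, and endoscopist experience is a secondary objective. Both reads and the CAD EYE output are recorded for each polyp. This stands: the gap is in the analysis, not in intent or data. It does not supply an estimate, a test or a named read. The expertise sub-analysis is optional and, as written, subdivides CAD EYE's performance without contrasting it with the endoscopist's.

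Two stronger readings should be resisted.

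- A reader might infer that 197 polyps is wrong or too few. The number reproduces from its stated inputs. The 12-point planning gap does exceed every gap in Expected Results (at most 8.9 points), but the required number also depends on a discordance and a comparator that the documents do not give.
- A reader might take it as an error rate that comparisons with experienced and with trainee readers would often disagree on significance. Those are two different questions with different true answers under the plan's own accuracies, and a trainee read is not guaranteed for every polyp. The error attributable to the gap is selective choice of read, roughly 9% against 5%.

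It is also fair to say that the serrated grouping is not a reviewer's choice. The Introduction describes serrated polyps as premalignant, and endoscopists record sessile serrated lesions separately, so imposing CAD EYE's grouping could change which method looks better.

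**Conclusion.** The point holds as a gap in the analysis plan and should be fixed before analysis. One of two primary objectives has no planned between-method estimate, and its comparator read is unnamed.

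That the choice of read matters follows directly from the printed accuracies: a gap of 1.2 points or of 7.7 to 8.9 points. The power and interval figures rest on assumed correlations of 0 to 0.5 and ignore clustering. The inflation from 5% to about 9% rests on equal accuracies of 0.78 and free choice between two reads; Expected Results assumes unequal accuracies, so it illustrates the risk and does not forecast it.

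A non-significant difference from experienced readers would not show comparability: with a 6 to 7% chance of significance at the expected gap, it is the likely result in any case.

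**What to change.** Add to Statistical analysis: *For each recovered polyp, CAD EYE and one pre-named endoscopist read (white light then BLI, system off) are each scored correct or incorrect against histology. The primary comparison is the paired difference in accuracy with a 95% CI allowing for several polyps per patient (for example a patient-clustered GEE or a cluster-adjusted McNemar test). Comparisons with the other reads are secondary.*

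The sponsor then settles, before analysis:

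- **The primary read:** performing, second (observing) or experienced endoscopist, or both reads jointly with clustering. If both readers are experienced, state which one counts as the experienced read.
- **Comparability:** if the experienced read is chosen, base any such conclusion on the CI against a pre-stated margin.
- **Scoring:** how sessile serrated lesions and other types are classed for endoscopist reads and histology, with the alternative grouping as a sensitivity analysis.
- **Sample-size wording:** relabel the two rates as unaided endoscopist and CAD EYE on the same polyps, say whose accuracy 0.70 is, and state the assumed discordance (for example 0.20 to 0.37).

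The cost is wording and slightly more analysis work; no added data or patients. There are trade-offs: a performing-endoscopist comparator reflects the unit's staffing mix, and an experienced comparator leaves the trainee comparison secondary.

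### The 197 polyps are sized on a 12-point gain, but Expected Results prints no gap above 8.9 points; if the undefined diagnostic ratio means accuracy, the stated 80% power is not supported for the gains the protocol expects

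*Combined protocol and SAP*

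**What the plan says.** The Sample size calculation sets the error rates ("For an alpha risk of 0.05 and beta risk of 0.2 for a bilateral test"), gives the number ("it will be necessary to include 197 colorectal polyps") and states its inputs, "assuming the initial pre-intervention diagnostic ratio is 0.7 and the final after-intervention ratio is 0.82". It does not define the ratio, name the readers behind the two values, or give a source for 0.82.

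Expected Results, the next section, anticipates for CAD EYE a "diagnostic accuracy in the optical characterization of colorectal polyps around 78.4"%, and describes it as "comparable to experienced endoscopists (78.4% vs 79.6%) and superior to less experienced endoscopists (70.7% vs 79.6"%).

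The comparison with endoscopists is a primary objective: accuracy in "optical characterization of colorectal polyps compared to digital chromoendoscopy". The readings are paired on the same polyp, being made "by the endoscopist in WLI and BLI modes, in a first phase and by the CAD EYE[®] with BLI, in a second phase" (Study design). Under Phase 2 of the detailed methods, two endoscopists read each polyp before CAD EYE does. At least one must be experienced, while "The two endoscopists should preferably (but not necessarily) be an experienced endoscopist and a trainee from the last few years". The Statistical analysis section lists accuracy, sensitivity, specificity and the two predictive values against histology, and names no test for CAD EYE against endoscopist reading.

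**The concern.** The effect used for sizing is 0.82 − 0.70 = 12 points. The expected accuracies do not contain such an effect. The largest printed gap is 79.6 − 70.7 = 8.9 points, and it becomes 78.4 − 70.7 = 7.7 points if CAD EYE takes the value the text gives it. No reader in Expected Results reaches 82%.

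The two brackets also do not fit together. In the first, 79.6% appears to belong to experienced endoscopists. In the second, it stands opposite less experienced endoscopists, where the CAD EYE value should be. So the expected gain over less experienced readers is either 7.7 or 8.9 points, depending on whose accuracy 79.6% is.

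At stake is the power statement for one of the two primary objectives. A reader will take 80% as the chance of detecting what the protocol expects to see, whereas it belongs to a larger gain that the protocol does not otherwise mention.

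**Working it through.** **Inputs.** Alpha 0.05 two-sided, power 0.80, 0.70 vs 0.82 and n = 197 come from Sample size calculation; 70.7%, 78.4% and 79.6% from Expected Results. The correlation of correctness between the two reads of a polyp is not in the documents; 0, 0.3, 0.5 and 0.7 are an assumed range (the highest feasible value is about 0.81 for 7.7 points and 0.79 for 8.9). Polyps are treated as independent.

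**Step 1: reproduce 197.** Two independent proportions, pooled variance, mean proportion 0.76:

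n = [1.960·√(2·0.76·0.24) + 0.842·√(0.70·0.30 + 0.82·0.18)]² / 0.12² = (1.184 + 0.503)² / 0.0144 = 197.7 per set of reads.

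Treated as 197 pairs with uncorrelated correctness, a McNemar test has 79.3% power for the same inputs. The plan's number is reproduced.

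**Step 2: power for the expected gains.** For accuracies p1 and p2 and correlation r:

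- both correct: p11 = p1·p2 + r·√[p1(1−p1)·p2(1−p2)]
- discordance: ψ = p1 + p2 − 2·p11
- with d = p2 − p1, power = Φ{[d√n − 1.960√ψ] / √(ψ − d²)}

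Worked at r = 0:

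- 70.7% vs 78.4%: p11 = 0.707·0.784 = 0.5543; ψ = 1.491 − 1.1086 = 0.3824; power = Φ[(1.081 − 1.212)/0.614] = Φ(−0.21) = 42%.
- 70.7% vs 79.6%: p11 = 0.5628; ψ = 1.503 − 1.1255 = 0.3775; power = Φ[(1.249 − 1.204)/0.608] = Φ(0.07) = 53%.

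Over the assumed range, with 197 pairs:

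| Correlation | 0 | 0.3 | 0.5 | 0.7 |
|---|---|---|---|---|
| 7.7 points: discordance | 0.38 | 0.27 | 0.20 | 0.12 |
| 7.7 points: power, uncorrected McNemar | 42% | 55% | 69% | 88% |
| 7.7 points: power, exact McNemar | 37% | 50% | 64% | 87% |
| 8.9 points: discordance | 0.38 | 0.27 | 0.19 | 0.12 |
| 8.9 points: power, uncorrected McNemar | 53% | 68% | 81% | 96% |
| 8.9 points: power, exact McNemar | 49% | 64% | 78% | 96% |

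The uncorrected rows use the formula above; the exact rows sum the binomial probabilities over the number of discordant pairs.

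**Step 3: what 80% would require.** With 197 pairs and the uncorrected test, the formula reaches 80% only if discordance is at most about 0.15 (7.7 points) or 0.20 (8.9 points). The limits are tighter for the exact test: at 8.9 points and discordance 0.19 it gives 78%.

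**Step 4: readers other than the less experienced.** Step 2 uses the lowest printed endoscopist accuracy and so the largest gain. For an assumed equal mix of experienced and less experienced readers:

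- CAD EYE 78.4%, experienced 79.6%: mix (70.7 + 79.6)/2 = 75.15%, gain 3.25 points, power about 12% to 28% over correlations 0 to 0.7.
- CAD EYE 79.6%, experienced 78.4%: mix (70.7 + 78.4)/2 = 74.55%, gain 5.05 points, power about 22% to 58%.

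Both ranges are for the uncorrected test.

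**The case against.** Four replies deserve an answer.

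*The 197 is correct.* It is. A reader might infer a calculation error, but Step 1 reproduces the number. The problem is the conflict between its input and the section that follows.

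*The ratio may not be accuracy.* The text does not say that it is, and Statistical analysis lists five measures. So it cannot be said flatly that a 12-point gain is excluded; that holds only if the ratio means accuracy. The reading is natural, since 0.70 lies next to the 70.7% for less experienced endoscopists. Nor does a gain from CAD EYE assistance fit, because Phase 2 describes no endoscopist re-read after CAD EYE is switched on. If another measure was meant, the protocol still has to name it.

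*The reads are paired, so power may be adequate.* This stands. At a correlation of 0.7, power is 88% or 96%. A reader might infer that the study is underpowered or needs more polyps; the documents do not support that, because they give no discordance. They equally do not support 80%.

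*Less experienced readers are not the primary comparison.* Also fair. Experience of the endoscopist is a secondary objective, and a trainee need not be present. But every other mix of readers gives a smaller expected gain, so this makes the stated power harder to defend, as Step 4 shows.

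**Conclusion.** The point holds as an inconsistency between a design assumption and the protocol's own expectation. If the ratio is accuracy, the 12-point sizing gain exceeds every expected gain, and 80% power is unsupported for those gains. The actual power is undetermined: 42% to 88% (7.7 points) or 53% to 96% (8.9 points) with the uncorrected test, and 37% to 87% or 49% to 96% with the exact test. These are the favourable figures, for less experienced readers; an assumed equal mix gives about 12% to 28% or 22% to 58%.

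The figures rest on an assumed correlation of 0 to 0.7, on 197 polyps carrying both reads, and on independence between polyps. Estimating CAD EYE accuracy against histology, the other primary objective, is not affected. This should be fixed, but it does not call the sample size itself into question.

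**What to change.** Keep 197 polyps.

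1. In Sample size calculation, state which measure, which comparison and which readers 0.70 and 0.82 refer to. Either justify 0.82 or replace it with the protocol's own expected value. In Expected Results, make clear whose accuracy 79.6% is.
2. In Statistical analysis, define one neoplastic/non-neoplastic rule for a correct read that serves both scales: endoscopists record hyperplastic, adenoma, sessile serrated lesion or other, while CAD EYE returns only hyperplastic or neoplastic. Without it, neither paired correctness nor discordance is defined. Name the McNemar variant (uncorrected or exact) for the primary comparison with endoscopist reading.
3. Replace the flat 80% with a conditional statement, for example: for an expected accuracy of [x]% for [reader] and [y]% for CAD EYE, with [n] polyps having both reads and a two-sided [variant] McNemar test at alpha 0.05, treating polyps as independent, power is [a]% to [b]% for discordance from [c] to [d].

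The cost is rewording of Statistical analysis, Sample size calculation and Expected Results. No patients or procedures are added. The stated power becomes conditional and less favourable.
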